2 PURPOSE OF THE STUDY AND STUDY OBJECTIVES

2.1 Purpose of the Study

Almost all NETs express sstr2, making these tumours a potential target for treatment with PRRT. Therefore, the scientific rationale is to use sstr2 specific overexpression as a mean to target the delivery of the radioactivity to the tumour cells. This characteristic of sstr2 targeting shows promise as a personalised treatment approach such as theranostic combining imaging and therapy. The SSA peptide component (OPS200) is the targeting moiety of the compound with selective high affinity for sstr2 (OPS201 IC₅₀=0.70 nM and ¹⁷⁷Lu-OPS201 dissociation constant (K_d=0.072 nM) and antagonistic behaviour, thus no signal transduction is expected by the binding of ¹⁷⁷Lu-OPS201 to sstr2.

¹⁷⁷Lu is the active moiety of the compound; it is a β minus emitting radionuclide, with a mean energy of 0.133 MeV and a mean penetration depth of 0.23 mm.[35] In addition to β-emission, ¹⁷⁷Lu has gamma rays which allow performing SPECT images and consequently dosimetry. Hence, the compound ¹⁷⁷Lu-OPS201 may offer a treatment option beyond standard of care for NETs where there are still unmet clinical and therapeutic needs (see Section 1.3.2.2).

The purpose of the phase I of the study is to evaluate the safety and tolerability of the compound ¹⁷⁷Lu-OPS201 in previously treated subjects with unresectable GEP NETs, Lung NETs and malignant, unresectable pheochromocytoma or paraganglioma as well as to recommend a treatment schedule for the phase II; i.e. recommended cumulative radioactivity and fractionation, dosing interval and peptide mass dose.

2.2 Study Objectives

The primary objective of the study is to assess the safety and tolerability of PRRT with ¹⁷⁷Lu-OPS201 administered in three cycles in subjects with sstr2 positive NETs (including phaeochromocytomas and paragangliomas).

The secondary objectives of the study are as follows:

- to evaluate the optimal radioactivity and peptide mass dose to be used in future studies;
- to characterise ¹⁷⁷Lu-OPS201 whole body biodistribution and PK of the radiopharmaceutical after each administration of ¹⁷⁷Lu-OPS201;
- to determine the radiation dosimetry of ¹⁷⁷Lu-OPS201 (organ exposure to administered radioactivity) after each administration of ¹⁷⁷Lu-OPS201 with three different peptide mass doses;
- to undertake a preliminary assessment of the therapeutic efficacy of ¹⁷⁷Lu-OPS201 PRRT by determination of RECIST v1.1 status;
- to evaluate the influence of ¹⁷⁷Lu-OPS201 PRRT on the subject's quality of life.

The exploratory objectives of the study are as follows:

CCI

- to determine the PK of OPS201 in plasma and urine;

CCI

CCI

2.3 Study Hypotheses

- (1) ^{177}Lu -OPS201 will be sufficiently safe to permit further clinical investigation when administered in previously treated subjects with unresectable GEP NETs, lung NETs and malignant, unresectable pheochromocytoma or paraganglioma.
- (2) Increase of peptide mass doses leads to improved tumour to background ratio for ^{177}Lu -OPS201 administration, with a possible positive impact on the safety profile with an increasing tumour to bone marrow ratio.

3 STUDY DESIGN

3.1 General Design and Study Schema

This is an open-label study to evaluate the safety and tolerability of ^{177}Lu -OPS201 for the treatment of NETs. This international, multicentre study is planned to be conducted in approximately 20 sites with distinguished experience in PRRT or comparable nuclear medicinal applications in Europe, USA and Australia.

The study will be performed in two parts, Part A and Part B.

Up to 55 subjects with histologically confirmed diagnosis of GEP NETs, lung NETs or pheochromocytoma or paraganglioma will be recruited in the trial:

- Part A: a minimum of six subjects and up to 15 subjects;
- Part B: a minimum of 25 subjects and up to 40 subjects.

Eligible subjects will receive three administrations (or up to 5 cycles in Part B; see Section 3.1.5) of ^{177}Lu -OPS201 at 8-week intervals (+2 weeks, or up to +4 weeks in case of AEs which have not adequately recovered (see Section 4.6)).

Subject safety and dose escalation (before initiating Part B) will be evaluated by an SRC in Part A and a DRB (Part B) (see Section 3.8 and Appendix 3).

The overall study design is shown in Figure 11, Figure 12 (Part A) and Figure 13 (Part B).

After signing informed consent, subjects will undergo screening (Screening Visit) up to 4 weeks before the first administration of ^{177}Lu -OPS201 to check enrolment eligibility criteria. A contrast enhanced CT/MRI scan (baseline for RECIST v1.1 evaluation) will be performed and a screening SRS will also be performed (unless already performed within 6 months prior to Visit 1 Day 1). Eligibility read for SRS and CT/MRI scans will be performed locally at screening. However, all images, including SRS, will be sent to the imaging core laboratory for later evaluation.

Although the visits are similar in Part A and Part B, there is a change in the amendment version 6.0 in the CT/MRI imaging which only affects Part B, hence visits for Part A and B are described separately. In both Part A and Part B, the end of the core study is defined as the End of Core Trial (EOCT) Visit of the last subject.

During the study, subjects will attend the following visits:

Part A

Visit 1: On Visit 1 Day 1, subjects will receive the first administration of ^{177}Lu -OPS201 followed by safety and extended dosimetry evaluations over 8 days, with additional laboratory safety tests repeated at Day 15 (± 2 days). At 4 weeks (± 5 days) after Visit 1 Day 1 (i.e. Follow-up Visit 1), the safety of the subjects will be assessed.

Visit 2: 8 weeks after Visit 1 Day 1 (+2 weeks or up to +4 weeks in case of AEs which have not adequately recovered) subjects will receive the second administration of ^{177}Lu -OPS201 followed by safety and dosimetry evaluations over 8 days, with additional laboratory safety tests repeated at Day 15 (± 2 days). At 4 weeks (± 5 days) after Visit 2 Day 1 (Follow-up Visit 2), the safety of the subjects will be assessed. Additionally, subjects will receive a CT/MRI scan to monitor the RECIST v1.1 status and tumour volume changes.

Visit 3: 8 weeks after Visit 2 Day 1 (+2 weeks or up to +4 weeks in case of AEs which have not adequately recovered), subjects will receive the third administration of ^{177}Lu -OPS201 followed by safety and dosimetry evaluations over 8 days, with additional laboratory safety tests repeated at Day 15 (± 2 days). At 4 weeks (± 5 days) after Visit 3 Day 1 (Follow-up Visit 3), the safety of the subjects will be monitored.

EOCT Visit: 8 weeks (± 5 days) after Visit 3 Day 1, the safety and efficacy of the treatment will be evaluated. Subjects enrolled in Part A after the protocol version (v6.0) comes into effect will receive a CT/MRI scan to monitor the RECIST v1.1 status and tumour volume.

Part B

[figure not shown]
Visit 1: On Visit 1 Day 1, subjects will receive the first administration of ^{177}Lu -OPS201 followed by safety and extended dosimetry evaluations over 8 days, with additional laboratory safety tests repeated at Day 15 (± 2 days). At Week 4 (Day 29 ± 5 days), Week 6 (Day 42 ± 5 days) (i.e. Follow-up Visit 1) and at intermediate timepoints, the safety of the subjects will be assessed.

Visit 2: 8 weeks after Visit 1 Day 1 (+2 weeks or up to +4 weeks in case of AEs which have not adequately recovered) subjects will receive a CT/MRI scan to monitor the RECIST v1.1 status and tumour volume. Subjects will then receive the second administration of ^{177}Lu -OPS201 followed by safety and dosimetry evaluations over 8 days, with additional laboratory safety tests repeated at Day 15 (± 2 days). At Week 4 (Day 29 ± 5 days), Week 6 (Day 42 ± 5 days) (Follow-up Visit 2) and at intermediate timepoints, the safety of the subjects will be assessed.

Visit 3: 8 weeks after Visit 2 Day 1 (+2 weeks or up to +4 weeks in case of AEs which have not adequately recovered), subjects will receive a CT/MRI scan to monitor the RECIST v1.1 status and tumour volume. Subjects will then receive the third administration of ^{177}Lu -OPS201 followed by safety and dosimetry evaluations over 8 days, with additional laboratory safety tests repeated at Day 15 (± 2 days). At Week 4 (Day 29 ± 5 days), Week 6 (Day 42 ± 5 days) (Follow-up Visit 3) and at intermediate timepoints, the safety of the subjects will be monitored.

EOCT Visit: 8 weeks (± 5 days) after Visit 3 Day 1, the safety and efficacy of the treatment will be evaluated. Subjects will receive a CT/MRI scan to monitor the RECIST v1.1 status and tumour volume. Subjects who are to receive additional cycles of therapy (see Section 3.1.5) will undergo the EOCT assessment after Cycle 3. Where possible, the EOCT visit and Visit 4, Day 1 of the first additional cycle can be combined.

Figure 11 Overview of Study Design for Part A and Part B and Post Study Follow-up

[figure not shown]
EOCT=end of core trial; W=weeks. *only for Part B

3.1.1 Part A Design

In Part A, it is planned to treat up to 15 subjects with three cycles of 4.5 GBq ¹⁷⁷Lu-OPS201. An SRC will decide, based on the dosimetry and safety data of the initial three and then six subjects, if the remaining nine subjects will continue at the same radioactivity level or if the radioactivity has to be adapted. Alternatively, Part A can be closed and Part B initiated.

Figure 12 shows the study design for Part A.

Figure 12 Study Design - Part A

3.1.2 Part B Design

Part B is a dose escalation both of peptide mass and radioactivity. Up to eight cohorts will be enrolled as described below, see Figure 13.

[figure not shown]
Part B will encompass radioactivity and peptide mass dose escalation as well as intra-individual peptide mass dose evaluation. It consists of up to eight cohorts. In each cohort, each subject will receive three cycles of the defined radioactivity and peptide mass dose of ¹⁷⁷Lu-OPS201

(see Section 6.2, Table 11). Each cycle will be 8 (+2) weeks apart. In case of AEs which are not adequately recovered, a further 4 weeks can be added between dosing.

After the three core-treatment cycles, up to two additional cycles of ^{177}Lu -OPS201 can be administered if the subject continues to meet the criteria outlined in Section 6.4.2 and the subject has clinical benefit (defined as CR, PR or SD). The additional cycles are optional and must be discussed with the sponsor before administration.

The population of Cohorts 3 and 6 will enrol eight to 10 subjects to ensure a minimum of eight completed subjects. All remaining cohorts (1, 2, 4, 5, 7 and 8) will enrol three to five subjects to ensure a minimum of three completed subjects per cohort (see Section 3.3). A completed subject is defined as one who has received at least 3 cycles of study treatment or fewer than 3 cycles if one of the following has occurred: exceedance of organ dose limits, treatment-related safety issues or disease progression.

Figure 13 Study Design - Part B

DRB=data review board; GBq=gigaBecquerel; SRC=safety review committee.

Each cohort consists of three cycles of treatment. Cohort 2 will not be conducted if 700 μg or 1300 μg peptide mass is shown to be optimal. Cohorts 7 and 8 will not be conducted if 1300 μg peptide mass is seen to be too high. Cohorts 3 and 6 require 10 subjects for eight to be completed. All other cohorts are three to five subjects (minimum of three subjects to be completed).

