Cohorts 3 and 6 will require 8 subjects to ensure there is sufficient power to demonstrate any tumour sstr2 saturation. Therefore 10 subjects will be enrolled to obtain a minimum of 8 completed subjects. All remaining cohorts (1, 2, 4, 5, 7 and 8) will enrol three to five subjects to obtain a minimum of three completed subjects per cohort.

Hence, it is anticipated that 10 subjects will be enrolled in Cohorts 3 and 6, and five subjects will be enrolled in Cohort 1, so the end-point can be achieved in these initial three cohorts rapidly (total of 25). To maintain the subject numbers to a maximum of 40 in Part B, if all remaining cohorts are utilised (total of five), each will have three subjects enrolled (total of 15).

Change in eligibility criteria for Part B

To ensure sufficient precision for the imaging dosimetry (specifically in Cohorts 3 and 6, but also for the whole study), eligibility will require a minimum of two lesions ≥ 20 mm in diameter. Tumour dosimetry should be performed on tumour lesions identified by the imaging core laboratory and on no more than five lesions (maximum two per organ, size ≥ 20 mm diameter, accessible for dosimetry). Furthermore, this ensures the modelling is based on a minimal total receptor burden.

Infusion rate

The i.v. infusion of ^{177}Lu -OPS201, should be at a rate of 10 mL/h over 120 minutes (see Section 6.2.1).

Investigators are advised that prophylaxis may be considered if the patient is thought to be at increased risk of infusion-related reactions as per the site's standard of care (see also 6.3.3 and Section 6.3.4). Appropriate treatment should be administered should an infusion-related reaction occur including somatostatin analogues. The administered radioactivity and mass dose follows the escalation scheme (see Section 6.2).

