Although a subject is not obliged to give reason(s) for withdrawing, if a subject is discontinued at any time after entering the study, the investigator should make a reasonable effort to ascertain the reason(s) while fully respecting the subject's rights. The investigator will make every effort to contact the subject and complete the termination status page on the eCRF and, if possible, conduct an EW Visit that will take place 8 weeks after the last administration study medication. In case of discontinuation of treatment/withdrawal from treatment as described in Section 6.4, the EW Visit and the Long-term Follow-up Visits will be performed as planned.

The reasons for treatment and/or study discontinuation should be collected and reported in the eCRF.

Appropriate follow-up of withdrawn subjects will be performed, as required. Attempts to contact subjects who withdraw from a study must be documented.

Withdrawn subjects will be replaced if they do not complete treatment (the first three cycles) due to any reason other than exceedance of organ dose limits, treatment-related safety issues or disease progression.

4.6.2 *Withdrawal Criteria for Optional Biobanking*

Subjects participating to the optional research biobanking program have the right to withdraw their consent at any time and for any reason during the study or during the period of sample storage (i.e. the entire 15 years during which the sample is kept). If a subject wishes to withdraw his consent for biobanking and the samples are still at the investigator site or at Central Laboratory at this time, the investigator must inform the study monitor in writing of the subject's decision and destroy the samples. The study monitor will forward confirmation of the destruction to Biomarker/Biobanking study monitor.

If the samples are at the sponsor's repository (biobanking vendor), the investigator must inform directly Ipsen using the e-mail address, **CCI**, mentioning only the subject study ID in this e-mail. Ipsen will ensure destruction of the samples and all corresponding aliquots and issue confirmation of the withdrawal, which will be forwarded to the investigator. Analyses conducted before the withdrawal will not be affected.

4.6.3 *Study or Site Termination*

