11.2 Sample Size Determination

It is anticipated that a total of up to 55 subjects will be recruited, up to 15 subjects in Part A and up to 40 subjects in Part B. This is considered appropriate for an exploratory study and it is not based on formal statistical sample size calculation. In the event subjects do not complete treatment due to any reasons other than exceedance of organ dose limits or treatment related safety issues, additional subjects may be recruited as replacements to ensure an adequate sample size in the “per protocol set” for safety evaluation. Subjects with noninterpretable dosimetry scans may be replaced upon agreement of the investigator and the sponsor.

For Cohorts 3 and 6 in Part B, to detect a difference between two peptide doses within the same cohort, the total sample size of eight is calculated. Assuming 30% standard deviation of the paired difference, there is 80% power to detect a 2-fold-change, and 99% power to detect a 3-fold change at a 2-sided alpha of 0.05.

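### In Cohorts 3 and 6, eight 'completed' subjects do not guarantee the eight within-subject peptide contrasts on which the stated power rests

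*Protocol*

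**What the plan says.** **Design.** In Cohorts 3 and 6 every subject receives 300 µg in Cycle 1, a higher mass in Cycle 2 only (700 µg in Cohort 3, 1300 µg in Cohort 6), and 300 µg again in Cycle 3 (Protocol 3.1.3; Protocol Table 11).

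**Size.** Protocol 3.1.3 states that "Cohorts 3 and 6 will require 8 subjects to ensure there is sufficient power to demonstrate any tumour sstr2 saturation". Protocol 11.2, repeated in SAP 1.3.7, adds that "to detect a difference between two peptide doses within the same cohort, the total sample size of eight is calculated". It continues "Assuming 30% standard deviation of the paired difference", and concludes that "there is 80% power to detect a 2-fold-change, and 99% power to detect a 3-fold change" at a two-sided alpha of 0.05.

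**Counting rule.** Protocol 3.1.2 and SAP 1.2.1.2 say: "A completed subject is defined as one who has received at least 3 cycles of study treatment or fewer than 3 cycles", provided the shorter course ended for one of three listed reasons. No minimum number of cycles is given. Protocol 3.1.2 allows eight to ten to be enrolled. Protocol 3.1.3 is firmer: "Therefore 10 subjects will be enrolled to obtain a minimum of 8 completed subjects".

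**Replacement.** Protocol 4.6.1 and SAP 1.3.5 replace subjects who fail to finish the three cycles "due to any reason other than exceedance of organ dose limits, treatment-related safety issues or disease progression". Protocol 11.2 and SAP 1.3.7 except only organ dose and treatment-related safety, so under those sections a subject who progresses can be replaced. Protocol 11.2 makes this optional; SAP 1.3.7 makes it definite.

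**The concern.** The sample size is in pairs and the recruitment target is in completed subjects. The two agree only if every completed subject reaches Cycle 2 and has usable dosimetry there. A subject stopped after Cycle 1 for a listed reason is completed, is not replaced under Protocol 4.6.1, and has no 300-versus-700 or 300-versus-1300 µg contrast.

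This can happen. Entry requires documented progression (Protocol 4.1, criterion 8), Part B schedules CT/MRI before the second dose (Protocol 3.1), and the Protocol 6.4.2 stopping criteria are checked before Cycle 2.

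The contrast matters because the second interim analysis uses Cohorts 3 and 6 to confirm the peptide dose and to decide whether Cohorts 2, 7 and 8 open (Protocol 11.6; SAP 3.2.17). SAP Table 9 also makes the decisions on Cohorts 7 and 8 depend on lesion receptor saturation in Cohort 6 Cycle 2. A cohort could be declared full with fewer contrasts than the plan says it needs.

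**Working it through.** **1. What a pair requires.** The SAP 3.2.2 analysis is the ratio of specific absorbed dose between visits, for example visit 2 to visit 1. That needs lesion dosimetry at Cycle 2 and at a 300 µg cycle. A stop after Cycle 2 keeps the Cycle 1–Cycle 2 pair; only a stop before Cycle 2 loses it.

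**2. Whether another rule enforces the pair.** The ITT-DAS asks for one complete dosimetry set, and the PP-DAS adds only the absence of relevant major violations (Protocol 11.1; SAP 2.3). Replacement for non-interpretable scans is optional and does not clearly cover a cycle never given. Nothing found requires eight subjects with both cycles.

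**3. The stated power.** Inputs from Protocol 11.2: n = 8, SD 30% of the paired difference, two-sided alpha 0.05, 2-fold and 3-fold changes. The scale and test are not given.

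Paired normal approximation on log10, SD 0.30: power = Φ(Δ√n / 0.30 − 1.96).

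- 2-fold: Δ = log10 2 = 0.301; 0.301 × 2.828 / 0.30 = 2.838; Φ(0.878) = 81.0%.
- 3-fold: Δ = log10 3 = 0.477; 0.477 × 2.828 / 0.30 = 4.498; Φ(2.538) = 99.4%.

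This matches 80% and 99%. Other readings at n = 8:

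| Reading | 2-fold | 3-fold | Match |
|---|---|---|---|
| Paired t, log10 SD 0.30 | 68.4% | 96.9% | no |
| Paired t, natural-log SD 0.30 | over 99.9% | over 99.9% | no |
| Two-sample t, natural log, CV 30%, 4 per group | 79.4% | 99.1% | yes, but not paired |

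**4. Power with fewer pairs.** The log10 column uses the step 3 formula. The natural-log column is a paired t-test with noncentrality ln 2 × √n / 0.30.

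| Pairs | log10, normal: 2-fold / 3-fold | Natural log, paired t: 2-fold |
|---|---|---|
| 8 | 81.0% / 99.4% | over 99.9% |
| 7 | 75.6% / 98.8% | not tabulated |
| 6 | 69.1% / 97.4% | 99.3% |
| 5 | 61.2% / 94.5% | 96.5% |
| 4 | 51.9% / 88.9% | 85.4% |

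**5. Chance of reaching eight pairs.** The documents give no rate of stopping before Cycle 2. Let q be that rate; 10–20% is assumed for illustration and 5–30% shows the range.

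- Ten enrolled: P(at least 8 of 10), binomial with success probability 1 − q.
- Closed at eight completed, every loss being for a listed reason: (1 − q)^8; for example 0.9^8 = 0.43 and 0.8^8 = 0.17. Expected pairs are 8(1 − q).

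| q | At least 8 pairs, 10 enrolled | 8 pairs, closed at 8 | Expected pairs of 8 |
|---|---|---|---|
| 5% | 99% | 66% | 7.6 |
| 10% | 93% | 43% | 7.2 |
| 20% | 68% | 17% | 6.4 |
| 30% | 38% | 6% | 5.6 |

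**The case against.** The best defence is that the plan already has a margin. Protocol 3.1.3 enrols ten, so two lost pairs can be absorbed, and the 43–17% figures describe a closure at eight that Protocol 3.1.2 permits but 3.1.3 does not anticipate. That stands, and the ten-subject figures are the ones to lead with.

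Early loss may also be rare. One 4.5 GBq cycle at about 0.1 Gy/GBq (Protocol 1.6) gives 0.45 Gy to marrow against a 1.5 Gy limit, so the organ-dose route before Cycle 2 is remote. Protocol 3.1.3 describes this activity as tolerated in Part A. Under Protocol 4.6.1 progression permits withdrawal but does not require it. This makes the rate uncertain; it does not close the gap in the rule.

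No formal testing is planned (Protocol 11.3; SAP 3.1.9). The practical loss is therefore in the precision of the visit ratios and in the peptide decision, not in a test result.

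Three stronger readings are tempting, and the documents do not support them:

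- *Early stopping is never replaced.* Protocol 11.2 and SAP 1.3.7 allow replacement after progression. The defect there is the conflict with Protocol 4.6.1.
- *The escalation cohorts fail in the same way, because one-cycle subjects could make up the three completed.* Cohort progression uses three evaluable subjects (Protocol 3.8), and the note to SAP Table 9 asks for three completed subjects for each completed cycle. A subject stopped for toxicity is informative about DLTs. The Grade 4 events after a second cycle came from a separate investigator-sponsored study (Protocol 1.4).
- *Power is really 68% at eight pairs.* That comes from a paired t-test on log10, which does not reproduce the plan's figure. It is a reason to ask for the scale and test, not a measure of this problem.

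**Conclusion.** The mismatch holds, as a missing guarantee. A reader might infer that eight completed subjects cannot yield eight pairs; they can, but the counting rule does not ensure it.

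Under the assumed 10–20% loss before Cycle 2, the planned ten subjects give at least eight pairs with probability 93–68%. The resulting power loss cannot be fixed from the documents. It is material on the log10 reading that reproduces the stated power (69.1% for a 2-fold change with six pairs) and small on the natural-log paired-t reading (96.5% with five). The mismatch itself rests on the text alone; its size rests on the assumed loss rate and the unstated scale and test.

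The replacement rules in Protocol 4.6.1 and SAP 1.3.5 conflict with those in Protocol 11.2 and SAP 1.3.7 for a subject who progresses, and must be reconciled.

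**What to change.** 1. In Protocol 3.1.2, 3.1.3 and 11.2 and in SAP 1.3.7, for Cohorts 3 and 6 only, count toward the eight only subjects with interpretable lesion dosimetry at both Cycle 1 and Cycle 2, within the eight to ten already allowed.
2. Report the number of pairs in each cohort and how many of those subjects also have Cycle 3.
3. If fewer than eight pairs result, report confidence intervals for the number obtained and do not cite the 80% and 99% power. This fallback is needed because recruiting beyond ten may not be possible: with all cohorts used, 10 + 10 + 5 + 15 = 40 already meets the Part B maximum.
4. State the scale of the 30% SD and the test behind the power figures.
5. Reconcile the replacement rules on progression.
6. Keep the present definition of a completed subject for safety, DLT and disposition purposes, and for the other cohorts, which use it for their own enrolment target.

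The cost is wording. No enrolment beyond the present range is required, although the cohorts may need to use all ten places and the stated power may look less favourable once its basis is given.
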